6.0 Inclusion Criteria

- 6.1 All patients diagnosed with Covid-19 will be registered on the study regardless of their severity, but only those who meet high risk criteria will be treated with steroids. Those who do not meet the criteria will only be registered with no need to collect further data except baseline labs and CT chest. They should sign the consent form and the data manager can collect the rest of the information.
- 6.2 Male or female patients of 21 years or older diagnosed with Covid-19 by PCR or by rapid serological test will be eligible. Diagnosis of Covid-19 will be established by means of either the PCR molecular test or with the rapid serologic test or both. (see figure 3)

We have learned recently that some cases produce IgG very early and presence of IgG doesn't mean that infection is late. Those who are IgM positive but PCR negative, will be considered as "suspicious for Covid-19"; however, if their clinical presentation is typical for Covid-19, (see below) they will be counted as a positive diagnosis. Those who are IgM positive but PCR negative, for purposes of analysis will be divided as "polysymptomatic" (2 or more symptoms characteristic of Covid-19) or "not polysymptomatic". The symptoms considered as characteristic are fever, cough, dyspnea, myalgia, diarrhea, anosmia/dysgeusia, malaise, headache, abdominal pain, neurological symptoms (paresthesiae, delirium etc).

- 6.2 a. Patients who have negative Covid IgG and IgM but whose PCR results are not available yet and who have typical symptoms of Covid-19 (see section 6.2 above), or who have typical CT chest findings such as ground glass opacities, will be considered eligible. If PCR later on turns to be negative, the patient will be retrospectively considered as ineligible.
- 6.3 Eligible patients will be registered on study on or before 10 days from first onset of symptoms. Patients whose symptoms started > 10 days ago; but who are not in respiratory failure are eligible if they are still symptomatic.
- 6.4 In order to be treated with methylprednisolone, they must meet at least two of the following criteria on or shortly before day 10 (but not before day 7)

 from first onset of symptoms, in order to avoid treatment during viral phase; if two criteria are met before day 7, patient is eligible but treatment should not start before day 7 of illness:
 - 6.4.1 Serum IL-6 \geq 10 pg/ml before day 10.
 - 6.4.2 Ferritin> 500 ng/ml before day 10.

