 - 6.4.3 D-dimer > 1 mg/L (1,000 ng/ml) before day 10.
 - 6.4.4 CRP > 10 mg/dL (100 mg/L) before day 10.
 - 6.4.5 LDH above normal before day 10.

- 6.4.6 Lymphopenia (absolute lymphocyte count <900) before day 10.
- 6.4.7 O₂ saturation <94% by pulse oximetry, but more than 91%, before day 10.
- 6.4.8 CT chest with evidence of infiltrate(s).
- 6.5 Interpretation of results of rapid and PCR molecular tests:
 - 6.5.1 Those with serological positive test but negative molecular PCR test will be analyzed based on the clinical context. See below.
 - 6.5.2 Those who present with at least 2 of the following typical symptoms of Covid-19 (cough, fever, dyspnea, diarrhea, anosmia) will be considered as likely cases of Covid-19 while those with one or less symptoms will be considered as unlikely cases but will still be considered evaluable. They will be analyzed separately.
 - 6.5.3 Those who are PCR positive and serology positive or negative will be considered as definitive cases.
- 6.6 The CALL score will be used in the analysis of all cases (11). This score represents a composite index based on presence of comorbidities, age >60, lymphopenia and elevated LDH. Those cases with a score >6 have greater than 50% risk for serious complications.
- 6.7 Simultaneous treatment will be allowed with the following drugs: remdesivir, hydroxychloroquine, azithromycin, vitamin C, doxycycline, colchicine, zinc and ivermectin. Patients who have received 1 single dose of dexamethasone or methylprednisolone will be eligible. **Their use is not considered as a basis for exclusion** from this trial.

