7.0 Exclusion Criteria

- 7.1 Any patient with life expectancy <1 month
- 7.2 Any patient who is oxygen dependent
- 7.3 Any patient with long standing history of severe COPD

- 7.4 Any patient who is chronically oxygen dependent because of previously existing lung disease
- 7.5 Anyone with severely uncontrolled diabetes despite adequate management.
- 7.6 Anyone with active serious bacterial infection such as septicemia or pneumonia.
- 7.7 Anyone receiving Tocilizumab (anti-IL-6 therapy) or plasma therapy
- 7.8 Any patient already receiving steroids for another pre-existing illness
- 7.9 Cases who are IgG positive but IgM negative, will not be considered eligible unless they are positive by molecular PCR test or symptoms are highly suggestive of Covid-19 (> 3 of the following: cough, dyspnea, anosmia, diarrhea, myalgia, ground glass infiltrate(s) in CT chest) within first 10 days of illness.

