8.0 Management and Dosing Regimen

- 8.1 Patients will be admitted to a regular room in the hospital (**not** ICU)
- 8.2 They will be monitored closely with vital signs every 8 hours to ensure their respiratory and cardiovascular status do not deteriorate.
- 8.3 Methylprednisolone 80 mg IV bolus injection will be given daily x 5 days starting upon day 1-3 of registration on trial. Patients who are stable with O2 sat >94% and no other indication for hospitalization will be treated as outpatient with methylprednisolone 80 mg p.o. x 5 days.

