10.0 Primary Response Criteria for patients receiving methylprednisolone

10.0.1 Clinical complete response criteria require all the following:

10.0.1.1	No need for ventilatory support at any point
10.0.1.2	Not oxygen dependent by day 28 of registration
10.0.1.3	Alive by day 28 from registration on trial
10.0.1.4	CT chest with minimal or no evidence of disease by day 28
	from registration

10.0.2 Clinical partial response criteria require that 2 of the following be present by day 14 of therapy:

10.0.2.1	No need for ventilatory support at any point
10.0.2.2	Not oxygen dependent by day 28 from registration on trial
10.0.2.3	CT chest stable to improve over baseline by day 28 from
	registration

10.1 Secondary Response Criteria:

- 10.1.1 Decrease of at least 25% in anyone of the following markers, if elevated at baseline: IL-6, ferritin, D-dimer, CRP or LDH by day 14
- 10.1.2 Improvement of absolute lymphocyte count in those presenting with lymphopenia. Improvement is defined as increase by 25 % or more by day 14.

11 Data Management

- 11.1 Patients will be registered after obtaining signed consent form.
- 11.2 Registration will be performed at Auxilio Mutuo by calling [contact] [name].

12 Statistical Analysis

- 12.0 Analysis will focus in comparing pre-treatment and post treatment values.

 Results will be analyzed using the intent to treat principle which in this case means that those cases who receive at least one dose of methylprednisolone will be considered evaluable.
- **12.1** Evaluable cases are considered as those who have clinical data for at least 1 subsequent day.
- 12.2 Due to the small sample size, non-parametric tests for matched data will be used.

13.0 REFERENCES:

- 1. Gautret, P., et al., *Hydroxychloroquine and azithromycin as a treatment of COVID-19:* results of an open-label non-randomized clinical trial. Int J Antimicrob Agents, 2020: p. 105949.
- 2. Chen, L., et al., *Convalescent plasma as a potential therapy for COVID-19.* Lancet Infect Dis, 2020. **20**(4): p. 398-400.
- 3. Carr, A.C., A new clinical trial to test high-dose vitamin C in patients with COVID-19. Crit Care, 2020. **24**(1): p. 133.
- 4. Zhou, F., et al., Clinical course and risk factors for mortality of adult inpatients with COVID-19 in Wuhan, China: a retrospective cohort study. Lancet, 2020. **395**(10229): p. 1054-1062.

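### Section 10 calls outcomes that need no improvement a response: every unchanged treated patient is at least a partial response, so these rates cannot be read as drug activity

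*Protocol*

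**What the plan says.** Entry state of a treated patient:

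- Section 7.2 excludes "Any patient who is oxygen dependent".
- Section 8.1 states "Patients will be admitted to a regular room in the hospital", not to intensive care. Section 8.3 treats stable patients as outpatients.
- Section 6.4 requires two of eight criteria. One is an infiltrate on chest CT (6.4.8); six are laboratory values. The saturation criterion (6.4.7) is below 94% "but more than 91%, before day 10", which lies above the failure threshold in section 4.0.

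Response rules:

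- Section 10.0.1: "Clinical complete response criteria require all the following". The four items are no ventilatory support at any point, not oxygen dependent by day 28, alive by day 28, and "CT chest with minimal or no evidence of disease by day 28".
- Section 10.0.2: two of three items suffice. They are no ventilatory support, not oxygen dependent by day 28, and "CT chest stable to improve over baseline by day 28". There is no survival item and no item on the section 4.0 event.
- Section 10.1, the secondary criteria, asks for a 25% change in a marker or lymphocyte count that was abnormal at baseline.

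The primary event in section 4.0 is O2 saturation below 91% or pO2 below 60 on room air. Section 5.3 assumes that more than 50% of patients would develop respiratory insufficiency untreated. Section 5.4 calls the treatment successful if at most 50% of high-risk patients fail. No target or reference rate is given for the section 10 categories.

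**The concern.** The items in 10.0.1 and 10.0.2 describe a state that many treated patients are already in when they enter. Continuing in that state to day 28 is counted as a response. Only the secondary criteria in 10.1 are built to require change from an abnormal baseline.

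This matters because the study is non-randomised. Its only untreated patients are those who do not meet the high-risk criteria, so they are no comparator for the treated group. Section 3.0 itself says that some patients recover spontaneously after the first phase, and section 6.7 allows several other drugs alongside. Section 12.0 centres the analysis on pre-treatment versus post-treatment values, yet ventilation, oxygen dependence and survival are at their best at entry and can only hold or worsen. A high rate under a heading that says *primary response* will be read as drug activity.

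**Working it through.** The protocol states no response rate, so there is no figure to reproduce. The check is first logical, then a matter of scale.

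**1. A patient who does not change to day 28**

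| State, held throughout | Complete response (4 of 4 needed) | Partial response (2 of 3 needed) |
|---|---|---|
| Off oxygen, CT with no or minimal disease | 4 of 4, met | 3 of 3, met |
| Off oxygen, larger infiltrate | 3 of 4, not met | 3 of 3, met |

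The first row can occur because two laboratory criteria suffice under 6.4. A patient without a pre-treatment CT still meets the ventilation and oxygen items, which is enough for partial response.

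**2. A patient who has the section 4.0 event**

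If never ventilated and off oxygen by day 28, this patient meets two of the three items whatever the CT shows. A failure on the primary objective is then a partial response.

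**3. Partial response or better with an inactive drug**

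Let p be the proportion with respiratory failure and s the share of failures that still meet two of three items. Patients without failure are taken to stay unventilated and off oxygen, so they all qualify:

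Rate = 1 − p + p × s

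The protocol gives only p > 50%. All other inputs are assumptions: 20% or 40% of failures ventilated; on oxygen at day 28 in 40% of ventilated and 10% of other failures; CT worse in 50% of failures, independently of oxygen status. Death is not modelled separately. Section 10.0.2 is headed day 14, but two of its items are set at day 28 and the only follow-up CT in section 2.0 is at day 28, so the items are read at day 28.

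- A ventilated failure must be off oxygen and have a stable CT: 0.6 × 0.5 = 0.30.
- An unventilated failure needs one of the two: 1 − 0.1 × 0.5 = 0.95.
- s at 20% ventilated: 0.2 × 0.30 + 0.8 × 0.95 = 0.82.
- s at 40% ventilated: 0.4 × 0.30 + 0.6 × 0.95 = 0.69.

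| p | 20% ventilated | 40% ventilated |
|---|---|---|
| 0.5 | 0.5 + 0.5 × 0.82 = 91.0% | 0.5 + 0.5 × 0.69 = 84.5% |
| 0.6 | 0.4 + 0.6 × 0.82 = 89.2% | 0.4 + 0.6 × 0.69 = 81.4% |
| 0.8 | 0.2 + 0.8 × 0.82 = 85.6% | 0.2 + 0.8 × 0.69 = 75.2% |

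A harsher assumed set is p = 0.7, 60% of failures ventilated, oxygen at day 28 in 80% and 40%, CT worse in 80%. Then s = 0.6 × (0.2 × 0.2) + 0.4 × (1 − 0.4 × 0.8) = 0.024 + 0.272 = 0.296, and the rate is 0.3 + 0.7 × 0.296 = 50.7%.

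The part that does not depend on s is the number who never fail: N × (1 − p). With 40 to 60 treated this is 20 to 30 patients at p = 0.5 and 8 to 12 at p = 0.8.

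**4. How far the categories separate an active drug from an inactive one**

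Use the first set of inputs and let the drug halve p from 0.5 to 0.25.

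- Partial or better: 91.0% to 0.75 + 0.25 × 0.82 = 95.5%; 84.5% to 0.75 + 0.25 × 0.69 = 92.3%. The gain is 4.5 to 8 points.
- Complete response in patients with a clear baseline CT, taking all to survive and a CT that has not worsened as clear: a failure qualifies with probability 0.8 × 0.9 × 0.5 = 0.36 or 0.6 × 0.9 × 0.5 = 0.27. The rate moves from 68% to 84%, or from 63.5% to 81.8%. The gain is 16 to 18 points.

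**The case against.** The strongest reply is that this is a prophylaxis trial. Prevention trials enrol patients who are free of the event, and under section 5.3 more than half are assumed to fail untreated, so staying as entered is the result sought. That stands. It supports an endpoint called freedom from progression; it does not support the label *response*, or counting a patient who had the primary event.

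A reader might infer that the criteria are already met at entry. They are not: the items run to day 28, and the ventilation item covers the whole follow-up. What is present at entry is the state, and the endpoint is whether it lasts. A reader might also infer that any unchanged patient is a complete response. That fails too, because a more than minimal infiltrate must clear to satisfy 10.0.1.4.

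Two further points stand. Success is decided by 5.4, not by section 10. And complete response in patients with a clear baseline CT does separate an active from an inactive drug to a useful degree under the inputs shown; the near-insensitivity belongs to partial response.

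**Conclusion.** The point holds as a matter of definition. Under 10.0.2 every treated patient who stays as entered is a partial response, and so are some patients who had the primary event. Under 10.0.1 an unchanged patient is a complete response only with no or minimal disease on the baseline CT; the documents do not give the share of such patients.

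The size is less certain. An inactive drug would give partial response or better in 84.5% to 91.0% at p = 0.5, 75.2% to 85.6% at p = 0.8, and about 51% under the harsher set. Only p > 50% comes from the protocol, which equates to no specific value; the ventilation, oxygen and CT inputs are assumed. It would be wrong to conclude that the rate must be above 80% without drug effect. What does follow is that, with no comparator and no reference rate, neither category can be read as evidence of efficacy. The trial's success rule in 5.4 is not affected by this point.

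**What to change.** In section 10:

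1. Keep the items, but report them as *free of progression by day 28* for all treated patients. Do not count a patient who had the section 4.0 event, and carry over the survival item that 10.0.2 lacks.
2. Report *response* separately, for patients with an infiltrate on the baseline CT, and require improvement on the day-28 CT. A stable scan is non-progression.
3. Show complete response split by baseline CT: clear or minimal, infiltrate, and no pre-treatment CT. The third group is needed because section 2.1.3 only prefers a CT before methylprednisolone, so the timing of the scan must be recorded.
4. State that these rates are descriptive and not evidence of efficacy.

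The day-14 heading of 10.0.2 has to be reconciled with its day-28 items at the same time.

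The cost is wording and one table split. Both CTs are already in the schedule, and no visit, procedure or treatment changes. The downside is a smaller denominator for response, out of 40 to 60 treated patients, and a lower reported response rate.

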4.0 Study Objectives and End Points

Primary Objective:

- 1- To decrease the rate of progression to hypoxemic respiratory failure in high risk patients with Covid-19, treated with prophylactic steroids during the first phase of the disease.
 - a. Hypoxemic respiratory failure is defined as:
 - 1. O_2 saturation of < 91% or pO_2 <60 on room air
- 2- To evaluate the rate of complications of patients observed without treatment.
 Complications include progression to respiratory failure or any other complication leading to hospitalization.

Secondary Objectives:

- 1. To determine % survival at 28 days from registration on this clinical trial
- 2. To determine if there is any improvement in inflammatory markers following treatment with corticosteroids.
- 3. To define the length of hospitalization
- 4. To determine the frequency of admissions to ICU.
- 5. To determine the percentage of patients who require ventilatory support.
- 6. To determine the rate of complications and progression to respiratory failure in patients with favorable features (i.e., those eligible for observation and not for therapy with methylprednisolone.)
 - a. To validate these results in an independent cohort of cases diagnosed as Covid-19 from our general hospital population.
- 7. We will evaluate the proportion of patients with clinical improvement, as defined by live discharge from the hospital, a decrease of at least 2 points from baseline on a modified ordinal scale (as recommended by the WHO R&D Blueprint Group), or both. [10]
 - 7.1 The six-point scale consists of the following categories:
 - (1) not hospitalized;

- (2) hospitalized, not requiring supplemental oxygen;
- (3) hospitalized, requiring supplemental oxygen;
- (4) hospitalized, requiring nasal high-flow oxygen therapy, noninvasive mechanical ventilation, or both;
- (5) hospitalized, requiring invasive mechanical ventilation, ECMO, or both; and
- (6) death.

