5.0 Investigational Plan

- 5.1 Overall Design: This is a pilot phase II exploratory study. It is a non-randomized study which will be carried out at Auxilio Mutuo Hospital and possibly at other institutions to be recruited.
- 5.2 We plan to enter a total of 100 200 patients with the expectation that at least 40-60 will be eligible for therapy with methylprednisolone in order to determine whether the risk of progressing to respiratory failure can be reduced by administering corticosteroids.
- 5.3 We assume that >50% of patients who meet the criteria for entry into this trial will develop respiratory insufficiency if left untreated.
- 5.4 If \leq 50% of patients with high risk develop respiratory failure we will consider the treatment as successful.

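### The set called intent to treat in section 12.0 is a treated set, so high-risk patients who fail before a first dose drop out of the success rule in section 5.4

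*Protocol*

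**What the plan says.** - **Analysis set (12.0, 12.1).** Section 12.0 invokes intent to treat and explains it as meaning that "those cases who receive at least one dose of methylprednisolone will be considered evaluable". Section 12.1 adds: "Evaluable cases are considered as those who have clinical data for at least 1 subsequent day". It does not say what the day is subsequent to, or whether the two conditions apply jointly.
- **Success rule (5.3, 5.4).** Section 5.3 begins: "We assume that >50% of patients who meet the criteria for entry into this trial" and goes on to say that these patients will develop respiratory insufficiency if untreated. Section 5.4 sets the cut at 50% or fewer: if no more than that share "of patients with high risk develop respiratory failure we will consider the treatment as successful". Neither mentions dosed or evaluable patients.
- **Failure (4.0).** Respiratory failure is an O2 saturation below 91% or a pO2 below 60 on room air. No time window is attached to the primary objective.
- **Time to first dose (6.4, 8.3).** Section 6.4 states: "if two criteria are met before day 7, patient is eligible but treatment should not start before day 7 of illness". Section 8.3 has methylprednisolone "starting upon day 1-3 of registration on trial".
- **Size and design (5.1, 5.2).** The study is non-randomized and expects that "at least 40-60 will be eligible for therapy with methylprednisolone".

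**The concern.** Intent to treat would keep every patient who entered the high-risk group, whatever happened next. A set that requires a first dose keeps only those who reached it, and the protocol builds in time during which a patient can fail first. A patient registered on illness day 2 who already meets two criteria waits until illness day 7, which is five days. If saturation falls below 91% in that time and no dose is given, the patient has met the primary failure definition but is not analysed. The observed rate is then judged against a cut written for all high-risk patients.

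The rule is a bare cut at 50%, set next to an assumed untreated rate of just over 50%, so a few exclusions can reverse the conclusion. There is no concurrent control group in which the same exclusion would occur.

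**Working it through.** **Inputs.** From the protocol: 40 to 60 patients for treatment (5.2), success if 50% or fewer fail (5.4), untreated rate above 50% (5.3). The protocol gives no exact untreated rate and no pre-dose failure rate. I therefore assume true failure rates p of 55% and 60%, and shares e of high-risk patients who fail before dosing and are dropped of 0%, 5% and 10%. The 40 to 60 has no stated derivation to reproduce; I use it only as a range.

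**Step 1: exclusions needed to reach 50%.** With F failures in n patients and k pre-dose failures dropped, the analysed rate is (F − k)/(n − k).

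- 22/40 = 55%: k = 4 gives 18/36 = 50%.
- 33/60 = 55%: k = 6 gives 27/54 = 50%.
- 24/40 = 60%: k = 8 gives 16/32 = 50%.
- 36/60 = 60%: k = 12 gives 24/48 = 50%.

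So 10% of high-risk patients is enough at a 55% rate, and 20% is needed at 60%.

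**Step 2: chance of declaring success.** The analysed failure probability is q = (p − e)/(1 − e), for example (0.55 − 0.10)/(1 − 0.10) = 0.50. With m = n(1 − e) patients analysed, success means that at least half of the m do not fail, and its probability is an exact binomial tail.

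| p | e | q | n = 40 | n = 60 |
|---|---|---|---|---|
| 55% | 0% | 55.0% | 0.316 | 0.258 |
| 55% | 5% | 52.6% | 0.435 | 0.345 |
| 55% | 10% | 50.0% | 0.566 | 0.554 |
| 60% | 0% | 60.0% | 0.130 | 0.075 |
| 60% | 5% | 57.9% | 0.205 | 0.114 |
| 60% | 10% | 55.6% | 0.306 | 0.246 |

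**Step 3: the opposite effect.** Undosed high-risk patients who recover also leave the set. If 22/40 loses four pre-dose failures and one undosed recovery, the rate is 18/35 = 51.4%, above the cut. With four such recoveries it is 18/32 = 56.3%, above the true 55%. The table therefore describes the loss of failures alone.

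**Step 4: timing.** Counting the registration day as day 1, a patient registered on illness day d reaches day 3 of registration on illness day d + 2. The day-7 hold in 6.4 and the day 1-3 window in 8.3 are both satisfied only if d + 2 ≥ 7, that is d ≥ 5. For earlier registration the two cannot both be followed.

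**The case against.** The primary objective in 4.0 concerns high-risk patients treated with prophylactic steroids, and section 10 is headed for patients receiving methylprednisolone. A treated set fits both, and 12.0 openly says what it means by the term. Section 5.3 refers to the criteria for entry, and 6.1 registers every diagnosed patient, so 5.3 does not clearly describe the high-risk group. The study is an exploratory pilot, and the illustration depends on assumed rates close to the cut.

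Much of this stands. A treated analysis is legitimate if it is named as such, 5.3 is ambiguous, and no pre-dose failure rate is documented. But 5.4, the only success rule, is written for high-risk patients, and 12.0 fixes a different set under a label that promises the wider one.

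Three stronger readings are tempting and not supported:

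- **That patients followed for one day count as non-failures.** Section 12.1 makes them evaluable and gives no outcome rule. A complete response under 10.0.1 needs day-28 status, so an early loss could not be shown to be one. Handling of unknown status may properly sit in a statistical analysis plan that is not at hand.
- **That failures just after the first dose are dropped.** A patient who fails and has next-day data stays in and counts as a failure. Only a patient with no later-day data, such as one who dies or is lost on the day of first dose, could drop out, and only if 12.0 and 12.1 apply jointly.
- **That every exclusion favours success.** Step 3 shows otherwise.

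**Conclusion.** The point holds in this form: the set labelled intent to treat is a treated set, it does not match the population of the success rule, and the protocol's own timing allows high-risk patients to fail before they can enter it. Losing those failures favours a declaration of success. At an assumed true rate of 55%, losing 4 of 40 or 6 of 60 patients this way is enough to reach the cut; at 60% it takes 8 of 40 or 12 of 60. The net bias depends on how many undosed patients recover, which the protocol does not allow one to estimate. The undefined reference day in 12.1 is a smaller, conditional route to the same loss.

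**What to change.** - **Denominator.** Apply the 5.4 rule to all registered, eligible patients who meet 6.4, dosed or not, after the retrospective PCR exclusion in 6.2a and the exclusions in section 7. Judge section 7 as of the time 6.4 is met, so that later deterioration does not remove a patient.
- **Events.** Count respiratory failure, as defined in 4.0, from the time 6.4 is met. The endpoint itself need not change.
- **One-day rule.** State what the day in 12.1 is subsequent to, and do not let the rule remove patients from this denominator. Show the result with unknown later status counted as failure, as a sensitivity analysis.
- **Label.** Call the at-least-one-dose set treated and report it as secondary.
- **Timing.** Reconcile 6.4 and 8.3 for patients registered early in the illness; which rule should govern is for the investigators to settle.

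For the analysis set, the cost is mainly wording in 12.0 and 12.1. Section 2.2 already schedules day 14 and day 28 assessments for patients eligible for methylprednisolone, so no visits are added. The observed failure rate is likely to be somewhat less favourable.

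### The only tests named in section 12 are matched pre/post tests, which do not address the primary failure-rate objective and cannot attribute marker changes to the steroid

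*Protocol*

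**What the plan says.** Section 12.0 sets the direction of the analysis: "Analysis will focus in comparing pre-treatment and post treatment values". Section 12.2 gives the method: "Due to the small sample size, non-parametric tests for matched data will be used". The protocol names no other test.

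Primary Objective 1 in section 4.0 is "To decrease the rate of progression to hypoxemic respiratory failure in high risk patients with Covid-19", with failure defined as "O_2 saturation of < 91% or pO_2 <60 on room air". Its benchmark is in section 5.3: "We assume that >50% of patients who meet the criteria for entry into this trial will develop respiratory insufficiency if left untreated". Section 5.4 adds the decision rule: if at most 50% "of patients with high risk develop respiratory failure we will consider the treatment as successful". Section 5.2 expects that "at least 40-60 will be eligible for therapy with methylprednisolone". No significance level, power or target rate is given.

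For the markers, section 10.1.1 defines a response as "Decrease of at least 25% in anyone of the following markers, if elevated at baseline" (IL-6, ferritin, D-dimer, CRP or LDH), by day 14. Section 6.4 requires at least two of eight criteria for treatment, five of which are cut-offs on these same markers. Section 2.2 confines follow-up laboratory tests to patients eligible for treatment. Under section 6.1, patients who do not meet the criteria contribute baseline laboratory values and a CT only.

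**The concern.** A matched test asks whether patients changed from their own baseline. The primary question is whether a post-baseline event rate lies below an external reference. Nothing in section 12 connects the named tests to the rule in 5.3 and 5.4, so an analyst following section 12 has no method for the main result, and one following 5.4 has a bare point estimate with no statement of uncertainty.

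For the markers, a matched test does validly describe change. What is at stake is how that change is read. Patients are chosen partly because these values were high, only values high at baseline are scored, a fall in any one is enough, and no untreated patients are re-measured. Chance variation, regression to the mean, natural course and the concomitant drugs allowed in 6.7 cannot then be told apart from a steroid effect, although the rule sits under a response-criteria heading.

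**Working it through.** **1. The plan's own figure.** The 40-60 treated patients in 5.2 cannot be reproduced, because no alpha, power or alternative rate is stated. The operating characteristics of the 5.4 rule can be computed.

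**2. The 5.4 rule alone.** P(success) = P(X ≤ n/2), with X ~ Binomial(n, p).

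| True failure rate | n = 40 (X ≤ 20) | n = 60 (X ≤ 30) |
|---|---|---|
| 50% | 0.56 | 0.55 |
| 55% | 0.32 | 0.26 |

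When exactly half of the patients fail, the 95% Clopper-Pearson interval is 33.8-66.2% (20/40) or 36.8-63.2% (30/60).

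**3. Section 12 applied literally to the primary event.** Respiratory failure is meant to be absent at entry. Section 6.3 says so for patients more than 10 days from onset; for the others it is implied by exclusion 7.2 and by the aim of preventing progression. Discordant pairs therefore run almost entirely from no failure to failure. If all k do, the exact two-sided McNemar p-value is 2 × 0.5^k.
- 12/40 failures (30%): 2 × 0.5^12 = 0.0005, towards worsening.
- 20/40 failures (50%): 2 × 0.5^20 = 0.000002, towards worsening.

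Both results are successes under 5.4.

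**4. A one-sample test on the same data.** For 12/40 against 50%, the one-sided exact binomial p = P(X ≤ 12 | n = 40, p = 0.5) = 0.008, with a 95% Clopper-Pearson interval of 16.6-46.5%. This answers the question in 5.3 and 5.4 and points the other way from step 3.

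The protocol states no alpha, so two assumed values are shown:

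| One-sided alpha | n | Maximum failures | Actual alpha | Power at true 30% | Power at true 40% |
|---|---|---|---|---|---|
| 0.05 | 40 | 14 (35.0%) | 0.040 | 0.81 | 0.32 |
| 0.05 | 60 | 23 (38.3%) | 0.046 | 0.94 | 0.45 |
| 0.025 | 40 | 13 (32.5%) | 0.019 | 0.70 | 0.21 |
| 0.025 | 60 | 21 (35.0%) | 0.014 | 0.84 | 0.26 |

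**5. The any-one-marker rule when nothing changes.** Assume a within-person log-scale SD s of 0.3 to 0.5 (not in the protocol) and no true change. The chance of a fall of at least 25% in one marker is q = Φ(ln 0.75 / (√2 · s)).
- s = 0.3: Φ(−0.678) = 0.249.
- s = 0.5: Φ(−0.407) = 0.342.

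With k independent elevated markers, the chance of at least one such fall is 1 − (1 − q)^k. For correlated changes, the same quantity comes from an equicorrelated normal model.

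| Elevated markers | Independent | Correlation 0.5 |
|---|---|---|
| 1 | 25-34% | 25-34% |
| 2 | 44-57% | 38-49% |
| 5 | 76-88% | 56-69% |

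This formula covers chance variation only. Regression to the mean from selecting high values is a separate source of apparent improvement, and natural course may act in either direction.

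**The case against.** The strongest reply is that the protocol never says a paired test will be applied to respiratory failure. Section 12.0 speaks of values, which reads most naturally as laboratory measurements, and the primary question has its own rule in 5.4. The test that goes with that rule is something a statistical analysis plan commonly supplies. Much of this stands. A reader might infer that the protocol commits itself to a wrong-direction primary test. The text does not support that: the McNemar result shows what a literal reading would produce, not a stated plan. What remains is that the protocol does fix a test family, does not limit it to markers, and leaves the primary rule without a test or interval.

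Nor is absence of failure at entry explicit for everyone; it is stated only for patients beyond day 10. A few baseline failures would make some pairs run the other way, but would not bring the 50% benchmark into a matched test.

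On the markers, a reader might infer that improvement is nearly certain without any drug effect. That is not supported either. Section 3.0 says the second phase brings rising markers, so untreated patients could worsen. Patients can also qualify through lymphopenia, saturation or CT with none of the five markers raised, and the 76-88% figure needs all five elevated and independent. Secondary objective 2 asks only about improvement following treatment, so the protocol makes no explicit causal claim, and it calls itself pilot, exploratory and non-randomized. The narrower point survives: without a comparator, the response rate cannot be interpreted as a steroid effect.

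Finally, a formal test lends precision to a 50% benchmark for which 5.3 gives no source. That is fair, and the benchmark should be labelled accordingly.

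**Conclusion.** The point holds in this form: section 12 names only matched pre/post tests, these do not address Primary Objective 1, and the 5.4 rule on its own is close to a coin toss (0.55-0.56) at the benchmark rate. That probability is exact binomial arithmetic from the protocol's own 50% and 40-60 patients. The success thresholds depend on an assumed alpha, and any conclusion from them is only as good as the assumed untreated rate.

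For the markers, the missing comparator and the lenient any-one rule are facts of the design. The size of the chance response is not: about 25-34% for one marker, 38-57% for at least one of two and 56-88% for at least one of five rest on an assumed log-SD of 0.3-0.5 and a correlation between 0.5 and 0. Stronger correlation would lower the figures for several markers.

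**What to change.** In section 12:
- Analyse the primary endpoint as the proportion of treated patients with respiratory failure, using a one-sample exact binomial test and Clopper-Pearson interval against the 50% in 5.3. State the alpha, and tie 5.4 to that test. At one-sided 0.05, success would need at most 14/40 or 23/60 failures.
- Match the interval to the test: a two-sided 90% interval goes with one-sided 0.05, a 95% interval with 0.025 (at most 13/40 or 21/60).
- State that 50% is an assumed benchmark.
- Limit matched non-parametric tests to the markers.

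In section 10.1.1, replace the any-one-marker response with the median percent change and 95% interval for each marker separately, labelled descriptive, with no claim of treatment effect.

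The cost is wording only; no new data are needed. The downside for the sponsor is a stricter success threshold (35.0% or 38.3% observed failures instead of 50% at one-sided 0.05), limited power if the true rate is near 40%, and a less favourable marker summary.
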